## 8 STATISTICAL METHODOLOGY

### 8.1 Study Subjects

#### 8.1.1 Subject Disposition

Subjects' disposition will be summarized for all the subjects. Subjects who discontinued will be summarized by reasons for discontinuation.

Randomization details and subject disposition will be listed for RAND. Screen failures and inclusion and exclusion criteria deviation at screening will be listed for All Subjects.

#### 8.1.2 Analysis Populations

Analysis populations will be summarized and listed for RAND.

#### 8.1.3 Protocol Deviations

Protocol Deviations will be listed for RAND.

#### 8.1.4 Demographic and Other Baseline Characteristics

The following demographic and other baseline characteristics will be used.

	Category	Descriptive
Sex	Male, Female	
Age (years)		Yes
Height (cm)		Yes
Weight (kg)		Yes
BMI (kg/m^2)		Yes
Race	American Indian or Alaska Native, Asian, Black or African American, Native Hawaiian or Other Pacific Islander, White, Other	
Ethnicity	Not Hispanic or Latino, Hispanic or Latino, Unknown	

Demographic and other baseline characteristics will be summarized for the SAF by study part and treatment.

Demographic data will be listed for the SAF and other baseline characteristics (including alcohol consumption) will be listed for the SAF for each part of the study.

### **8.1.5 Medical History**

Medical history data will be listed for the RAND.

### **8.1.6 Prior or Concomitant Medications**

Prior and concomitant medication will be listed for the RAND.

### **8.1.7 Study Drug Administration**

For Part 3, study drug administration will be listed for RAND.

## **8.2 Safety Assessments**

Safety assessments will be made for the SAF. All safety data will be listed.

### **8.2.1 Adverse Events**

An overall summary including the following will be presented by study part.

- Subjects with at least one TEAE
- Subjects with at least one TESAE
- Subjects with at least one adverse drug reaction
- Subjects with at least one TEAE leading to discontinuation of study drug

The following summaries also will be conducted.

- TEAEs by SOC and PT
- TEAEs by SOC, PT and relationship to study drug

Each of the summaries will be done at the subject level - multiple occurrences of the same event within a subject will be counted once in the summaries by SOC and PT; multiple occurrences of the same event within a subject will be counted once in the maximum severity category (severe > moderate > mild) and/or maximum drug relationship category (reasonable possibility/no reasonable possibility). If intensity or relationship is found to be missing, the most severe occurrence will be imputed for that particular summary.

All AEs will be listed.

The above TEAE summaries will be produced for each dose level and placebo. For Part 2, all TEAEs will be tabulated in incidence tables by treatment (MT-6435 or placebo) as described above by fasting status. For subjects in Part 2, any AEs occurring in the first (fasting) period during Part 1 will be assigned to Part 1 until the time of dosing in Part 2. Therefore any AEs that occur during the washout period will be assigned to Part 1.

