## Europe/Mitsubishi Tanabe Pharma Europe Ltd

## STUDY PROTOCOL

	
Statistical methods:	
Sample size:  The sample size is not based on a formal statistical evaluation but was considered to be adequate to meet the objectives of the study and is a typical size for first-in-man SAD and MAD studies. A sufficient number of subjects will be screened to ensure that the planned sample size will be achieved.
 
Safety evaluation  AEs will be considered as treatment-emergent if they occur on or after the first dose administration of IMP or if a pre-dose event increases in severity following dosing. The frequency and incidence of treatment-emergent AEs (TEAEs) will be summarised by System Organ Class and Preferred Term for each dose level and by fed state, gender and race category where appropriate. Summaries will also be presented by relationship to treatment and severity of event. Serious TEAEs and TEAEs leading to discontinuation will be listed.  Safety laboratory test results, vital signs, and ECG parameters will be summarised by planned sampling point and for each dose level and by fed state, gender and race category where appropriate. Other safety measurements will be summarised and/or listed according to the data type.
 
Pharmacokinetic data  All data will be listed.
 
(i) Plasma and urine concentration of MT-6345  Plasma MT-6345 concentrations will be summarised by dose level, planned time point and by fed state, gender and race where appropriate using descriptive statistics.  By-subject plasma concentration versus time will be plotted as well as the mean concentration, for each dose level, and by fed state, gender and race where appropriate, using linear and semi-logarithmic scales. The concentration of MT-6345 in urine will be listed for Part 3.
 
(ii) Urine pharmacokinetic parameters of MT-6345  Urinary excretion and percent urinary excretion during each collection interval will be listed. Ae, Ae% and CLR will be summarised by dose level where appropriate, using descriptive statistics.
 
(iii) Plasma pharmacokinetic parameters of MT-6345  The PK parameters will be derived by non-compartmental analysis using WinNonlin® software (version 6.2 or later).  The PK parameters will be summarised for each dose level and by fed state, gender and race category where appropriate and time of dosing using descriptive statistics.
 
(iv) Dose proportionality (Part 1)  The PK parameters (AUC0-∞, AUC0-last and Cmax) from the SAD part will be used in the exploration of dose proportionality. The overall dose proportionality will first be evaluated using the power model. A linear model will be used to fit the power model, after log-transformation of the parameter of interest (e.g., AUC [AUC0-∞, AUC0-last] or Cmax). The model will include the log-transformed dose as fixed effect.

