**2.2 Study endpoints**

**2.2.1 Primary endpoints**

**Safety assessments**

- Incidence and severity of adverse events (AEs).
- Vital signs (supine blood pressure, pulse rate, respiratory rate and oral body temperature).
- ECG parameters (including heart rate and cardiac intervals: PR, QRS, QT and calculation of corrected QT interval using Fridericia's formula [QTcF]).
- Clinical laboratory assessments (including haematology, biochemistry, coagulation and urinalysis).
- Physical examination.
- Part 3 only, in addition: specialist eye examination findings

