**10.3.4.1 Adverse events**

A by-subject AE data listing including start/stop times, verbatim term, Preferred Term, SOC, dose level, severity, seriousness, relationship to treatment and outcome will be provided. All AEs that start before dosing but do not worsen after dosing will be classified as baseline AEs and will be listed only. All TEAEs, i.e., AEs which start on or after dosing, will be tabulated. In the tabulations, numbers of subjects with TEAEs and numbers (occurrences) of TEAEs will be counted separately. The frequency and incidence of TEAEs will be summarised by fed state, gender and race category where appropriate.

The following summaries of TEAEs will be presented:

- Summary of AEs by SOC and Preferred Term.
- Summary of AEs by SOC, Preferred Term and severity of event.
- Summary of AEs by SOC, Preferred Term and relationship to treatment.

The above TEAEs summaries will be produced for each dose level and placebo for Part 1 and for each dose level and placebo for Part 3. For Parts 2, 4 and 5, TEAEs will be presented by each dose of MT-6345 and placebo separately, alongside the corresponding dose and placebo from Part 1.

Serious TEAEs and TEAEs leading to IMP discontinuation will be listed.

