## 10 CHANGE FROM THE PROTOCOL

The planned analyses below were not done.

- Summary of AEs by SOC, Preferred Term and severity of event
- Summary of the change from baseline for vital signs, 12-lead ECG and routine safety laboratory tests
- A linear mixed model analysis for log-transformed PK parameters
- All analyses for Part 4 or 5

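### Protocol 10.3.4.1 asks for event counts beside subject counts in the TEAE tables; SAP 8.2.1 tabulates subjects only, and SAP Section 10 does not declare the change

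*SAP*

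**What the plan says.** Adverse events come first among the primary endpoints (Protocol 2.2.1; SAP 2.2.1), which name their incidence and severity.

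On how they are to be tabulated, Protocol 10.3.4.1, under the analysis of the primary endpoint, states: "In the tabulations, numbers of subjects with TEAEs and numbers (occurrences) of TEAEs will be counted separately". It then names three TEAE summaries: by SOC and Preferred Term, by those plus severity, and by those plus relationship to treatment.

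SAP 8.2.1 sets one counting unit for all its AE tables: "Each of the summaries will be done at the subject level". It adds that "multiple occurrences of the same event within a subject will be counted once in the summaries by SOC and PT". The breakdown is by dose: "The above TEAE summaries will be produced for each dose level and placebo". The same section also provides for every AE to be listed.

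SAP Section 1 gives the SAP precedence over the protocol on analysis details. SAP Section 10 introduces its list of changes with "The planned analyses below were not done". Its only item specific to AE tables is "Summary of AEs by SOC, Preferred Term and severity of event".

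**The concern.** The protocol asks for two numbers in each TEAE table and the SAP produces one. Because the SAP takes precedence, the protocol sentence cannot be read back into the tables. Because Section 10 itemises what was dropped and leaves this out, someone who relies on it would assume that the remaining AE tables follow the protocol.

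What is at stake is how tolerability is described at each dose. The cohorts are small: 6 active subjects planned per Part 1 cohort and 9 per Part 3 cohort. A percentage of so few subjects is coarse, and whether an affected subject had an event once or repeatedly is useful information that the percentage cannot carry. The severity table has also been dropped, so the SOC/PT tables show neither how severe the events were nor how many there were. They show only how many subjects were affected, split by relationship in one of them.

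**Working it through.** The point rests on no sample size, power or error rate, and the plan has no figure to reproduce. The check is a comparison of texts, followed by a small illustration.

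1. **What the protocol requires.** The sentence in 10.3.4.1 separates subjects from occurrences and applies to the tabulations. The by-subject listing is specified separately in the same section, so the listing does not satisfy this requirement.

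2. **What the SAP provides.** In 8.2.1 each line of the overall summary counts subjects with one or more events of the given kind. The SOC/PT and relationship tables count a repeated event once per subject. SAP 6.1 sets the percentage denominator as subjects in the treatment group, and the column layouts in SAP 9.2 are headed by numbers of subjects. No event-count column or table appears in the available SAP text.

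3. **Which text governs.** SAP Section 1 makes SAP 8.2.1 operative.

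4. **Whether the change is declared.** Of the protocol's three TEAE summaries, the SAP keeps two and Section 10 declares the third (severity) dropped. The change of counting rule inside the two retained tables is not mentioned there.

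5. **When a row loses information.** Let N be the subjects in a column, s the subjects with at least one event in the row, and E the number of events in the row. The SAP prints s and 100 × s/N. The protocol would also print E. The number of events not shown is E − s, which is zero unless some subject contributes more than one event to that row.

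| Hypothetical row, N = 6 (planned Part 1 active arm) | s | s/N | E | E − s |
|---|---|---|---|---|
| One event in each of 2 subjects | 2 | 33.3% | 1 + 1 = 2 | 0 |
| Five events in each of 2 subjects | 2 | 33.3% | 5 + 5 = 10 | 8 |
| One event in 1 subject | 1 | 16.7% | 1 | 0 |
| Five events in 1 subject | 1 | 16.7% | 5 | 4 |

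   The first two rows print identically under SAP 8.2.1, as do the last two. With the 9 active subjects planned for a Part 3 cohort, the first pair would both print as 2 (2/9 = 22.2%).

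6. **What can be recovered.** SAP 6.1 says that listings carry treatment, SAP 8.2.1 lists every AE, and the protocol's AE listing includes dose level and start and stop times. SAP 3.3.2 gives 44 subjects in Part 1 and 8 in Part 3, so 44 + 8 = 52 randomised; the 6 in Part 2 are returning Part 1 subjects. E can be counted by hand from listings of that size.

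**The case against.** The strongest reply is that little is lost. Incidence, which the endpoint names, is still tabulated by dose. The number of occurrences is not part of the endpoint's definition. No inferential safety analysis is planned (Protocol 10.3.4), so no estimate, test or interval changes. All of this stands.

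Four stronger readings might be inferred, and the documents do not support them:

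- **Repeat events cannot be seen by dose.** They are missing from the tables only. The listings show them with treatment.
- **Every row is affected.** Where no subject contributes more than one event, events equal subjects and nothing is missing. Parts 1 and 2 are single-dose, so repeats are less natural there. Part 3 is the plausible place, but only one cohort of 8 was enrolled, active and placebo combined. The five-event cases above are invented to show the mechanism and predict nothing.
- **The change is hidden.** The subject-level rule is stated openly in the section that governs the tables. Section 10 is framed as a list of analyses not done, and at the level of named summaries its AE entry is complete. Protocol 10.3.1 also has deviations described and justified in a separate document and in the study report, neither of which is available here. What can be said is only that the SAP's own list of changes omits it.
- **The synopsis independently requires event counts.** It says "The frequency and incidence of treatment-emergent AEs (TEAEs) will be summarised by System Organ Class and Preferred Term for each dose level". This is weak support, because Protocol 10.3.1 uses frequency for the ordinary count beside a percentage, so n (%) of subjects could satisfy it. The requirement rests on the one explicit sentence in 10.3.4.1.

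The reply does not remove the conflict itself. A requirement written for tabulations is not met by a listing, and a general precedence clause neither discloses nor justifies this particular departure.

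**Conclusion.** The concern holds in a limited form. Occurrence counts required by Protocol 10.3.4.1 are absent from all by-dose TEAE tables in SAP 8.2.1, and SAP Section 10 does not say so. This is a reporting gap and an undeclared departure; the primary endpoint is not lost.

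Its size is E − s in each affected row and zero in the others. It cannot be quantified further, because the documents give no event data. The loss is greater than it would otherwise be because the severity table has gone too.

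This rests on two assumptions: that the redacted SAP text contains no AE event-count output, and that the listings are produced as described. The importance is low. The study was terminated early, 52 subjects were randomised, and the missing counts can be rebuilt by hand. It is worth correcting mainly because doing so costs almost nothing.

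**What to change.** Add the number of events beside n (%) of subjects in the overall, SOC/PT and SOC/PT-by-relationship tables, as Protocol 10.3.4.1 states. Subject counts can keep the existing rule of one count at the maximum relationship category. Event counts would place each AE under its own recorded relationship. The SAP 8.2.1 rule that assigns washout AEs to Part 1 should apply to both counts.

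The cost is one extra column per table and the associated programming, using data already collected.

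If the column is not added, SAP Section 10 should state that occurrence counts are not tabulated, that repeat events can be found in the AE listings, and why this was chosen. The study report should carry the same statement, in line with Protocol 10.3.1.

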### 8.2.2 Laboratory Tests

Laboratory test reference ranges will be listed.

Absolute values will be summarized and listed at each timepoint for each study part by dose level and by fed state for the following parameters.

Laboratory Test	Parameters
Haematology	Haemoglobin, Haematocrit, Platelet Count, Red Blood Cell Count, Mean Corpuscular Haemoglobin (MCH), Mean Corpuscular Haemoglobin Concentration (MCHC), Mean Corpuscular Volume (MCV), White Blood Cell Count and Differential
Biochemistry	Alkaline phosphatase, Aspartate aminotransferase, Alanine aminotransferase, Gamma-glutamyl transpeptidase, Potassium, Sodium, Chloride, Inorganic phosphate, Glucose, Urea, Bilirubin (direct and total), Cholesterol, Triglycerides, High density lipoprotein-cholesterol, Low density lipoprotein-cholesterol, Protein (total), Albumin, Creatine kinase, Creatinine, Follicle stimulating hormone (FSH)  , Human Chorionic gonadotrophin (hCG) 
Coagulation	Prothrombin time, International normalised ratio, Activated partial thromboplastin time
Urinalysis	Specific gravity, pH, Protein, Glucose, Ketones, Urobilinogen, Blood, Human chorionic gonadotropin (hCG)  , Microscopic examination 

 Females only; performed at Screening only

 Females only; a serum pregnancy test will be performed at Screening and a urine pregnancy test at all other time points

 Performed only if required, based on urinalysis results

### 8.2.3 Vital Signs

Absolute values will be summarized and presented at each timepoint for each study part by dose level and by fed state for the following parameters.

- Systolic Blood Pressure (mmHg)
- Diastolic Blood Pressure (mmHg)
- Heart Rate (bpm)
- Respiratory Rate (breath/min)
- Oral Body Temperature (°C)
- Overall evaluation

All data will be listed.

### 8.2.4 12-Lead ECGs

Absolute values will be summarized and presented at each timepoint for each study part by dose level and by fed state will for the following parameters.

- PR (msec)

- QRS (msec)
- QT (msec)
- QTcF (msec)
- Overall evaluation

The frequency counts and percentages of subjects with 12-lead ECG values outside pre-defined limits will be summarized

All data will be listed.

### **8.2.5 Physical Examinations**

Physical examination body systems examined at Screening and Follow-up will be

- Head
- Ears/Nose/Throat
- Abdominal
- Cardiovascular
- Respiratory
- Dermatological
- Musculoskeletal
- Neurological
- Eyes
- General appearance
- Neck
- Lymph Nodes
- Other

Abbreviated physical Examination body systems examined at all other visits.

All data will be listed.

### **8.2.6 Eye Examinations**

Eye examination data will be listed.

## **8.3 Pharmacokinetics Evaluation**

### **8.3.1. Plasma and Urine Concentration**

Plasma MT-6345 concentrations will be summarized at each nominal sampling point by dose group for single dose group, multiple dose group and food state. All plasma and urine concentrations will also be listed.

Plots for single dose group;

For each dose group and food state, individual plasma concentrations vs. actual time for 0-24hr and 0-t hr (t: last sampling time point) will be plotted on both linear/linear and log/linear scales for MT-6345. Mean plasma concentrations vs. nominal time curves for 0-24hr and 0-t hr will be plotted on both linear/linear (+SD) and log/linear scales overlaid by all dose groups MT-6345. Plots will also be prepared overlaid by food state, as appropriate.

Plots for multiple dose group;

For each dose group, individual plasma concentrations vs. actual time will be plotted on both linear/linear and log/linear scales for MT-6345. Mean plasma concentration vs. nominal time curves will be plotted on both linear/linear (+SD) and log/linear scales overlaid by all dose groups for MT-6345. Plots will also be prepared overlaid, as appropriate.

The following mean plots for MT-6345 will be produced:

- Day all: plots on linear/linear (+SD) scale and log/linear scales
- Day 1: plots on linear/linear (+SD) scale for 0-24 hr

### 8.3.2. Pharmacokinetic Parameters

The pharmacokinetic parameters listed in Section 2.2 will be calculated for each subject on active dose using a non-compartmental model. The pharmacokinetic parameters will also be listed. The plasma pharmacokinetic parameters will be summarized by each dose group and fed state. The plasma pharmacokinetic parameters will also be listed for each part.

The urinary pharmacokinetic parameters will be summarized for each dose level. The urinary pharmacokinetic parameters will also be listed.

### 8.3.3. Dose Proportionality

Dose proportionality will be assessed by  $AUC_{0-\text{last}}$ ,  $AUC_{0-\infty}$  and  $C_{\max}$  for single dose using a power model. A schematic representation of this is outlined below:

$$AUC_{0-\text{last}} \text{ or } AUC_{0-\infty} \text{ or } C_{\max} = e^{\mu} \cdot Dose^{\beta} \cdot e^{\varepsilon}$$

The following linear model will be fitted to the log-transformed parameters of interest:

$$\log_e (AUC_{0-\text{last}} \text{ or } AUC_{0-\infty} \text{ or } C_{\max}) = \mu + \beta \cdot \log_e (Dose) + \varepsilon$$

Where  $\mu$  and  $\beta$  are the regression intercept and slope coefficients and  $\varepsilon$  is the error term; assumed to be normally distributed.

The estimate obtained for  $\beta$  is a measure of dose proportionality. Dose proportionality will be

concluded if the 95% CI for  $\beta$  includes the value 1. The parameter estimates and the 95% CIs will be produced.

The evaluation of the model fit will be done by lack-of-fit. In the case where dose-proportionality across all investigated dose groups cannot be established, additional exploratory analysis will be done by either fitting power model on subgroup of investigated dose groups or other data-driven analysis, if deemed appropriate.

To evaluate dose proportionality graphically the following plots will be produced:

- Individual plots of  $AUC_{0\text{-last}}$ ,  $AUC_{0\text{-}\infty}$  and  $C_{\max}$  versus dose levels on linear and log scales (with the fitted linear regression line for log scales)
- Individual plots for  $AUC_{0\text{-last}}/\text{dose}$ ,  $AUC_{0\text{-}\infty}/\text{dose}$  and  $C_{\max}/\text{dose}$  by dose level

